Participants will complete a within-subjects online randomized experiment. After providing informed consent, participants will view and rate messages on perceived message effectiveness (primary outcome) and perceived awareness of the harms of social media (secondary outcome). Participants will view messages about 9 topics: 8 warning topics and 1 control topic. The 8 warning topics include 7 potential mandatory social media warnings (including the topics of depression and anxiety, body image, addiction, sleep, mental health harms to children, not been proven safe, and California's proposed warning) and 1 voluntary warning (similar to a message used on TikTok to encourage users to take breaks). For each topic, participants will view 1-2 messages and respond to survey items about that message. All messages will be shown in random order.

Statistical Considerations

General Principles

We will use a two-sided critical alpha of 0.05 as a criterion for all tests of statistical significance. All confidence intervals presented will be 95% and two-sided. We will follow intention-to-treat principles, including all participants who fully enroll in the study. We expect minimal missing data based on prior similar studies¹⁻³ but missing data will be accounted for under maximum likelihood assumptions in our mixed effects regression analysis of primary and secondary outcomes.

Primary Outcome

The primary outcome is perceived message effectiveness for discouraging social media use. We will measure perceived message effectiveness with 1 item adapted from prior studies,^{4,5} “How much does this message discourage you from wanting to use social media?” Response options will range from not at all (1) to a great deal (5).

Secondary Outcomes

The secondary outcome is reported increased awareness of the harms of social media. We will measure perceived awareness of the harms of social media with 1 item, “How much does this message increase your awareness of the harms of using social media?” Response options will range from not at all (1) to a great deal (5).

Statistical Methods

We plan to present results in two papers.

Paper 1 Analyses

1. Analyses of the primary outcome

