- c. We will **descriptively rank the social media warning topics** on the secondary outcome of perceived awareness of the harms of social media. We will estimate mean perceived awareness of the harms of social media for each topic (averaging across messages for each topic) and rank those means.

Paper 2 Analyses

1. Analyses of the primary outcome:

- a. We will test whether the effects of the social media warning topics in this study with human participants differ from the effects observed in a separate experiment conducted with artificial intelligence (AI) personas. We will compare the coefficient on each warning topic estimated in this study to the corresponding coefficient estimated in the separate experiment conducted with AI personas. We will pool data from this study with the data from the separate experiment conducted with AI personas and run a mixed effects linear regression, regressing perceived message effectiveness on indicator variables for each warning topic (excluding the control as the referent), an indicator variable for sample (i.e., whether the observation is from this study vs. the AI study), and the interaction between warning topic and sample. All variables will be centered. We will examine the coefficients on the interaction terms.

- b. We will compare how our human participants rate social media warnings we refined using AI personas to those we selected *a priori* and did not refine using AI. We will make this comparison both overall (pooling across all warning topics) and within each warning topic. These analyses will only include ratings from the 6 warning topics for which we tested both AI-developed and human-developed messages (depression and anxiety, negative body image, addiction, sleep, mental health harms to children, and not been proven safe).
 - i. First, we will use mixed effects regression, regressing perceived message effectiveness on an indicator variable for message source (AI-developed vs. human-developed) and treating the intercept as random. The coefficient on the indicator variable will indicate the average difference in means between AI-developed vs. human-developed messages.

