 - ii. Second, we will run a set of mixed effects regressions, one for each warning topic. Each regression will regress perceived message effectiveness on an indicator variable for message source (AI-developed vs. human-developed), treating the intercept as random. The coefficient on the indicator variable will indicate the average difference in means between AI-developed vs. human-developed messages.

Sample Size Needs

We plan to collect data from 1,000 participants. We used G*Power⁶ to estimate sample size needs to detect an effect of each social media warning topic vs. control using ANOVA repeated measures (testing of within-subject factors). Assuming alpha=0.05, 2 measurements (given each contrast will compare 2 topics to one another), and a conservative correlation among repeated measures of 0.5 (based on prior studies⁷⁻⁹), a sample size of 900 would yield 85% power to detect effects of $f=0.05$ ($d=0.10$) or larger. This effect size would be considered small¹⁰ and is conservative based on our prior message development studies.^{8,9,11} We will recruit 1,000 participants to account for potential missing data.

Exclusions and Outliers

We will exclude human participants who do not complete the survey or who complete the survey implausibly quickly (defined as <1/3 of the median completion time). We will winsorize outlier values defined as more than 3 interquartile ranges below or above the 25th and 75th percentiles of the observed distributions (i.e., Tukey far outliers). These participants and winsorized observations will be included in the analysis.

References

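### The pooled human-AI regression should not rely on the default single residual variance: interaction standard errors are wrong if the two samples differ in both size and spread

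*SAP*

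**What the plan says.** Paper 2 Analyses, 1.a, sets out the human-AI comparison in two steps. It first states the aim: "We will compare the coefficient on each warning topic estimated in this study to the corresponding coefficient estimated in the separate experiment". It then gives the method, which is to "pool data from this study with the data from the separate experiment conducted with AI personas and run a mixed effects linear regression". The fixed terms are the topic indicators, a sample indicator and their interactions. The output is stated as "We will examine the coefficients on the interaction terms".

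The section gives no residual variance by sample, no random-intercept variance by sample and no robust or clustered standard errors. It does not restate the random intercept, which is described for the Paper 1 models and for Paper 2, 1.b. General Principles applies a "two-sided critical alpha of 0.05" to all significance tests. The Introduction calls the human-AI comparison a secondary goal.

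For the human sample, Sample Size Needs says "We plan to collect data from 1,000 participants" and bases power on 900. No size or standard deviation is given for the AI experiment.

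**The concern.** The model lets people and personas differ in mean rating but, by default, not in variability. Its residual variance is then an average over both samples, dominated by the larger one, and that average is used for both halves of the interaction standard error. The plan gives no reason to expect software personas to scatter around their own mean as people do, and it does not tie the number of personas to the number of participants.

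The validity of the interaction tests is at stake. If the larger sample is the less variable one, human-AI differences are declared too often. If the larger sample is the more variable one, the tests are too conservative and real differences are missed. In either case the p-values depend partly on how many personas were run.

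**Working it through.** **The plan's own figure.** Sample Size Needs says "a sample size of 900 would yield 85% power to detect effects of" f = 0.05 (d = 0.10), with two measurements and "a conservative correlation among repeated measures of 0.5". The noncentrality is 900 × 2 × 0.05² / (1 − 0.5) = 9, with 1 and 899 degrees of freedom. Power is 0.850, so the 85% reproduces. It concerns a topic-versus-control contrast in humans; the SAP states no power or precision for the human-AI interaction.

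**Inputs for the interaction.**
- Human sample: n_h = 900, the SAP's power figure.
- Two-sided alpha: 0.05, from General Principles.
- Assumed, because the SAP does not give them: n_a personas, from 100 to 5,000, and r, the AI-to-human ratio of within-rater SD, from 0.25 to 1.25.
- Also assumed: complete data, the same message set for every rater, and no true human-AI difference.

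**Formulas.** With complete data the random intercept cancels from each topic-minus-control contrast. Write s_h² and s_a² for the two residual variances. Up to a constant set by the number of messages per topic, which cancels in the ratio below:
- correct variance: s_h²/n_h + s_a²/n_a
- common-variance model: [(n_h s_h² + n_a s_a²)/(n_h + n_a)] × (1/n_h + 1/n_a) = s_h²/n_a + s_a²/n_h
- correct minus reported: (s_h² − s_a²)(1/n_h − 1/n_a)

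The common-variance model in effect divides each variance by the other sample's size. The gap is zero only if the spreads are equal or the sizes are equal. With s_h = 1 and s_a = r, let k be the square root of reported over correct variance. The type I error is then 2Φ(−1.96k).

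**Worked case: 5,000 personas, r = 0.5.**
- Correct: 1/900 + 0.25/5,000 = 0.001161
- Reported: 1/5,000 + 0.25/900 = 0.000478
- k = √(0.000478/0.001161) = 0.641
- Type I error: 2Φ(−1.257) = 0.209

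**Range, 900 humans:**

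| Personas | SD ratio | k | Type I error |
|---|---|---|---|
| 100 | 0.5 | 1.687 | 0.1% |
| 100 | 1.25 | 0.837 | 10.1% |
| 900 | 0.5 | 1.000 | 5.0% |
| 1,000 | 0.25 | 0.955 | 6.1% |
| 1,000 | 0.5 | 0.969 | 5.8% |
| 1,000 | 1.25 | 1.012 | 4.7% |
| 2,000 | 0.5 | 0.793 | 12.0% |
| 5,000 | 0.5 | 0.641 | 20.9% |
| 5,000 | 1.25 | 1.166 | 2.2% |

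**Check by simulation.** These runs used 1,000 humans, 15 messages (assumed) and 1,500 runs per scenario. With 5,000 personas and r = 0.5, the common-variance standard error averaged 0.026, against an observed SD of the estimate of 0.040; type I error was 20%. With 200 personas it was 0.5% at r = 0.5 and 13% at r = 1.5. With separate variances, it was 3.9% to 5.3% in all six scenarios. One fitted mixed model (300 humans, 1,500 personas, r = 0.5) reported a standard error of 0.0475; the separate-variance value was 0.0730.

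**The case against.** **The common variance is not SAP text.** This stands. Item 1.a names a mixed effects linear regression and lists its fixed terms. Sample-specific variances or clustered standard errors would be compatible with those words. A reader might infer that the analysis is wrong as written, but the document supports only that the ordinary default of the named model is unsafe here and that nothing in the text departs from it.

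**Whether any error will occur is unknown.** This also stands. Both size and spread must differ, and the SAP reports neither for the AI sample. If about 1,000 personas were run, the effect is negligible. The larger figures need thousands of personas, or a small and more variable AI sample.

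**The direction is not fixed by the persona count.** A reader might infer that running fewer personas than people means real differences are missed. That holds only if personas vary less than people; 100 personas with 1.25 times the SD gives too many false positives instead.

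**The family-wise figure looks alarming.** For 5,000 personas and r = 0.5, the chance of at least one false difference among eight interactions sharing a control is about 72%, against 25% with correct standard errors. Much of that comes from running eight unadjusted tests. The SAP openly forgoes adjustment as exploratory, although it says so under Paper 1. The per-test figures are the fairer measure.

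**The spurious differences may be small.** Take the human residual variance as 0.5 SD², in line with the plan's correlation of 0.5, and one rating per topic. At 5,000 personas and r = 0.5 the 95% half-width is then 1.96√0.000478 = 0.043 SD instead of 1.96√0.001161 = 0.067 SD. The extra false positives therefore lie below the d = 0.10 that the plan calls small. This limits the practical harm in that case, but does not cover small AI samples with larger spread.

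**Conclusion.** The point holds as a conditional one. Under the default single residual variance, the interaction standard errors in Paper 2, 1.a, are wrong exactly when the human and AI samples differ in both size and within-rater spread. Across the assumed cases tabulated, per-test type I error runs from 0.1% to 21%, and it is about 5-6% when the samples are of similar size.

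The documents do not show that an error will occur, or in which direction. That rests on the size and spread of an experiment the SAP does not describe, and on the model being fitted with its defaults. The matter is confined to one secondary-goal analysis. Interaction point estimates are unbiased, and the Paper 1 comparisons, Paper 2, 1.b, and the sample size are untouched. This is an improvement available at no cost, not a demonstrated fault in the results.

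**What to change.** Add one sentence to Paper 2, 1.a, choosing one of these:
- keep the pooled model, but let the residual and random-intercept variances differ between human and AI samples;
- keep the pooled model and use standard errors clustered on participant or persona;
- fit the topic model separately in each sample and compare coefficients by z = (b_human − b_AI)/√(SE_human² + SE_AI²), which is closest to the aim 1.a itself states.

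Report each human-AI difference with its 95% confidence interval, and state the number of personas.

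The cost is one sentence and one model option. No new data are needed, and with complete data the interaction estimates do not change. If the samples turn out alike in size or spread, the results will be essentially the same as under the default.

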 - a. We will use mixed effects linear regression to **evaluate the effect of each warning topic compared to the control topic on the primary outcome of perceived message effectiveness**. We will regress perceived message effectiveness on a set of indicator variables representing each social media warning topic (e.g., depression and anxiety, negative body image, sleep, etc.), excluding the control topic as the referent. We will treat the intercept as random to account for repeated measures within participants. The coefficients on the warning topics will give the average difference in mean perceived message effectiveness between each warning topic and the control topic. Given the exploratory nature of the study, we do not plan to correct *p*-values for multiple comparisons.
 - b. We will use the same mixed effects linear regression model to **evaluate the effect of each potential mandatory warning topic compared to the voluntary warning**.

- c. In exploratory analysis, we will test whether the effects of the warning topics on the primary outcome are possibly moderated by age (treated continuously), gender (male vs. female), and amount of social media use (treated continuously). To test for moderation, we will use mixed effects linear regression, regressing perceived message effectiveness on indicator variables representing each social media warning topic (excluding the control as the referent), the possible moderator, and the interactions between the possible moderator and the warning topics. We will center variables prior to analysis. We will use separate models for each moderator. We will test the joint significance of the interaction terms.
- d. We will also **descriptively rank the warning topics** on the primary outcome of perceived message effectiveness. We will estimate mean perceived message effectiveness for each social media warning topic (averaging across messages for each topic) and rank those means.

2. Analyses of the secondary outcome:

- a. We will use mixed effects linear regression to **evaluate the effect of each social media warning topic compared to the control topic on the secondary outcome of awareness of the harms or social media**. We will use the same approach as described for the primary outcome (see no. 1 above).
- b. We will use the same mixed effects linear regression model to **evaluate the effect of each potential mandatory warning topic compared to the voluntary warning**.

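### Paper 2 item 1.a asks whether topic effects differ between human participants and AI personas, but plans no joint test of the eight interaction terms to answer that overall question

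*SAP*

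**What the plan says.** Paper 2 Analyses, item 1.a, opens with an inferential aim: "We will test whether the effects of the social media warning topics in this study with human participants differ" from those seen in a separate experiment with AI personas. Its next sentence plans a comparison of each topic's coefficient with its AI counterpart. The two datasets are pooled in a mixed effects linear regression with topic indicators (control as referent), a sample indicator and topic-by-sample interactions. The item then closes: "We will examine the coefficients on the interaction terms".

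Four other places in the SAP bear on this:

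- **Study Protocol:** "Participants will view messages about 9 topics: 8 warning topics and 1 control topic". With control as referent, there are eight interaction terms.
- **General Principles:** "We will use a two-sided critical alpha of 0.05 as a criterion for all tests of statistical significance".
- **Paper 1, item 1.a:** "Given the exploratory nature of the study, we do not plan to correct" p-values for multiple comparisons.
- **Paper 1, item 1.c (moderation by age, gender and amount of use):** "We will test the joint significance of the interaction terms".

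Paper 2 item 1.b makes its comparison of AI-refined and unrefined messages both overall and within topic.

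**The concern.** Item 1.a asks two things. One is topic by topic: does this topic's effect differ between the samples? The other is overall: do the effects differ? The eight coefficients answer the first. Nothing in the item answers the second, and no rule says how eight results become one conclusion.

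Paper 1 item 1.c has the same structure, with a moderator in place of sample, and there the SAP does plan the joint test. Paper 2 item 1.b has an overall step beside its within-topic step. Item 1.a has only the topic level, and no reason is given.

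What is at stake is the headline of the human-versus-AI comparison. With no rule fixed in advance, one term crossing 0.05 by chance could be written up as a general difference. Equally, eight non-significant terms could be written up as agreement. The estimates themselves are not at fault.

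**Working it through.** **The plan's own figure.** The only quantitative figure nearby is the 85% power in Sample Size Needs (N=900, f=0.05, 2 measurements, correlation 0.5, alpha 0.05). The noncentrality is f² × N × m / (1 − ρ) = 0.0025 × 900 × 2 / 0.5 = 9.0. With F(1, 899) this gives 85.0%, so the figure reproduces. It concerns one topic against control among human participants and does not bear on the human-versus-AI comparison. The SAP gives no error rate for item 1.a.

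**Inputs for the check.**

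- Alpha 0.05, two-sided, for each term (General Principles).
- Eight interaction terms (Study Protocol).
- Messages per topic: "For each topic, participants will view 1-2 messages and respond to survey items about that message". The number for the control topic is not given.
- Paper 2 item 1.b: "These analyses will only include ratings from the 6 warning topics for which we tested both AI-developed and human-developed messages". Those six topics therefore have at least two messages. I assume one each for the California and voluntary warnings, and vary the control between one and two.
- Further assumptions: the random-intercept model is correct, and the AI experiment uses the same topics and message layout.

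**Correlation between terms.** Every contrast uses the same control ratings, so the eight terms are positively correlated. Let topic j have m_j messages and the control m_0. Under a random-intercept model, each contrast has variance proportional to 1/m_j + 1/m_0, and two contrasts have covariance proportional to 1/m_0. Hence

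corr(j, k) = (1/m_0) / √[(1/m_j + 1/m_0)(1/m_k + 1/m_0)].

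The sample sizes enter only through a common factor, so the unknown number of personas cancels.

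- One message everywhere: 1/2 = 0.50 for every pair.
- Six topics with two messages, two with one, control with one: from 1/2 = 0.50 (both one-message) to 1/1.5 = 0.67 (both two-message).
- Same topics, control with two: from 0.5/1.5 = 0.33 to 0.5/1 = 0.50.

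**Chance that at least one of eight terms has p<0.05 when none truly differs** (1,000,000 simulated sets per layout):

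| Layout | At least one of eight |
|---|---|
| One message per topic, control one | 25.1% |
| Six topics with two, two with one, control one | 21.4% |
| Six topics with two, two with one, control two | 26.2% |

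More extreme layouts run from 20.1% (all topics two, control one) to 29.3% (all topics one, control two). If the tests were independent it would be 1 − 0.95⁸ = 33.7%; the shared control brings it down.

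**Joint test.** On 200,000 of the same draws per layout, the 8-df Wald test of all eight terms rejects in 4.9% to 5.0% of sets. That is the nominal 5% within simulation error, whatever the layout.

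**The case against.** The strongest reply is that item 1.a is mainly a topic-level analysis. Its second sentence plans a coefficient-by-coefficient comparison, and the interaction terms are exactly those estimates. A joint p-value would not say which topics differ. Paper 1 item 1.c has no such per-coefficient sentence, so it is not an exact precedent. The lack of correction is disclosed and justified by the exploratory nature of the study, and the human-versus-AI comparison is called a secondary goal. All of this stands. It limits the point to the overall question, which the opening sentence still poses.

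A reader might infer that the plan as written carries a 21-26% chance of a false finding. The SAP does not support that. The figure needs a rule that any one significant term means an overall difference, and the SAP contains no such rule. Each topic-level claim keeps its 5% error rate.

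A reader might also infer that the comparison is underpowered, or that agreement will be claimed wrongly. The SAP does not give the number of personas, so no power figure follows from it, and it plans no claim of agreement. Nor should the d=0.10 of the sample-size section be taken as a margin for agreement. It is a detectable topic-versus-control effect; using it that way would be an equivalence test with a borrowed margin.

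Finally, a joint test does not change the chance that one of eight unadjusted intervals excludes zero. It settles only which result answers the overall question.

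**Conclusion.** The point holds in a limited form. Item 1.a poses an overall question along with eight topic-level ones and provides an analysis only for the latter, while the SAP plans a joint test for the same type of interaction elsewhere. If one significant term were read as an overall difference, the chance of that with no true difference would be about 21-26% across the layouts that best fit the SAP, against 5% for a joint test. These figures rest on a correct random-intercept model, the same topics and layout in the AI experiment, and the assumed message counts for the California, voluntary and control topics. No multiplicity correction is called for, and the topic-level estimates and intervals stand as planned. Severity is minor: an optional, cheap improvement.

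**What to change.** In Paper 2 item 1.a, after the sentence on the interaction coefficients, add wording to this effect:

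*The eight topic-by-sample interactions will be tested jointly (8-df Wald or likelihood-ratio test), and this test will answer whether effects differ overall. Each topic's human-minus-AI difference will then be reported with its 95% CI as the topic-level result. A non-significant difference will not be taken as evidence of agreement.*

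The cost is one extra test from the model already planned and this short addition to the text. It needs no new data and no p-value correction. The downside is that a real difference confined to one topic may be reported as secondary when the joint test is not significant.

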Complete Title: An evaluation of social media warning labels for teens and young adults: A randomized controlled trial

Short Title: Reactions to social media warning labels

Protocol Date: August 1, 2025

NCT #: 07199660

Study Principal Investigator:

[name]
Stanford University
email: [contact]

Protocol Synopsis

Study Title	Social Media Warning Labels
Funder	NA
Clinical Phase	NA
Study Rationale	
Among teens and young adults, average daily social media use is high and contributes to poor mental health and other adverse outcomes. Warning labels are a low-cost, highly scalable strategy for informing consumers about product harms and discouraging unhealthy behaviors.It remains unknown how teens and young adults respond to social media warnings, including which warning topics may be most effective at discouraging social media use and raising awareness of the harms of social media.
Study Objective(s)	The primary objective is to evaluate whether different social media warnings are perceived as effective at discouraging social media use and raising awareness of the harms of social media. A secondary objective is to compare perceived message effectiveness of warnings refined using artificial intelligence (AI) vs. those not refined using AI.
Study Design	Within-subjects randomized experiment.
Subject	Inclusion Criteria
Population	1. 13 to 29 years old
key criteria for key criteria for	2. Reside in the US
Inclusion and Exclusion:	3. Can read and speak English
Number of Subjects	1,000
Study Duration	Each subject's participation will last approximately 10 minutes. The enrollment period is expected to last ~4 weeks.
Study Phases	There are two phases: (1) Screening : screening for eligibility and obtaining consent and (2) Intervention : study intervention/experimental treatment.
Efficacy Evaluations	The primary outcome is perceived message effectiveness for discouraging social media use. It is measured with 1 survey item. The secondary outcome is perceived awareness of the harms of social media use. It is measured with 1 survey item.
Statistical and Analytic Plan	Primary outcome 
First, we will examine the effect of each social media warning topic on perceived message effectiveness compared to control.Second, we will examine the effect of each potential mandatory social media warning topic compared to a voluntary social media

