warning. Third, we will test whether the effects of the social media warning topics in this study with human participants differ from the effects observed in a separate experiment conducted with artificial intelligence (AI) personas. Fourth, we will compare social media warnings we refined using AI personas to those we selected *a priori* and did not refine using AI.

Secondary outcomes

- We will examine the effect of each social media warning topic on awareness of the harms of social media compared to the control topic. We will also examine the effect of each potential mandatory social media warning topic compared to a voluntary social media warning.

Data and Safety Monitoring Plan

- The principal investigators are responsible for data quality management and ongoing assessment of safety.

Introduction

The primary goal of the analyses described here is to use data we collected through an online randomized experiment to examine consumer responses to different social media warning messages. These analyses examine the effect of warning topic (e.g., depression and anxiety, body image, sleep) on perceived message effectiveness (primary outcome) and perceived awareness of the harms of social media (secondary outcome).

A secondary goal of the analyses described here is to test whether the effects of the social media warning topics in this study with human participants differ from the effects observed in a separate experiment conducted with artificial intelligence (AI) personas. Another secondary goal is to examine whether warnings refined using AI are perceived as more effective than those selected *a priori* and not refined using AI.

This analysis plan pre-specifies the analyses before collecting data and therefore serves as our ex-ante planned analysis.

Study Protocol

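### Paper 2, analysis 1b(i): the pooled AI-versus-human test takes its standard error from a participant random intercept alone, so for the tested messages that SE may be too large or too small; a participant-level difference cures this at almost no cost

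*SAP*

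**What the plan says.** The Protocol Synopsis (Study Objective(s)) makes the AI comparison a secondary objective: "A secondary objective is to compare perceived message effectiveness of warnings refined using artificial intelligence (AI) vs. those not refined using AI". Paper 2, analysis 1b, sets it out: "We will compare how our human participants rate social media warnings we refined using AI personas to those we selected" in advance without AI. The data are restricted: "These analyses will only include ratings from the 6 warning topics for which we tested both AI-developed and human-developed messages".

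Two models follow. Analysis 1b(i) is the overall test, pooled over the six topics, "regressing perceived message effectiveness on an indicator variable for message source (AI-developed vs. human-developed) and treating the intercept as random". Analysis 1b(ii) repeats the comparison topic by topic: "Each regression will regress perceived message effectiveness on an indicator variable for message source (AI-developed vs. human-developed), treating the intercept as random". The grouping factor of the intercept is not restated in 1b; Paper 1, analysis 1a, shows that it is the participant. Analysis 1b(i) names no topic term, no participant-level source or topic effect, and no robust variance.

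On the design, the Study Protocol section says "For each topic, participants will view 1-2 messages and respond to survey items about that message". Together with the restriction to topics that have both kinds of message, this suggests one AI and one human message in each of six topics, all rated by every participant. That is an inference; the SAP does not state it outright.

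**The concern.** A random intercept makes all twelve ratings from one person equally correlated. That holds only if topics do not differ in mean rating, participants do not differ in how they react to particular topics, and participants do not differ in how much they prefer AI texts.

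The SAP itself expects some of this variation. Paper 1 estimates and ranks separate topic means, and its analysis 1c asks whether topic effects vary with age, gender and social media use. The first is topic variation; the second is a form of participant-by-topic variation. Both cancel from a source contrast made within topic, yet 1b(i) leaves them in the residual that sets its SE. A varying preference for AI texts acts the other way: it does not average out over a person's six pairs, and the model treats it largely as if it did.

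At stake are the interval and p-value of the one overall test of a stated secondary objective. The point estimate is not affected when data are complete.

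**Working it through.** **The SAP's own figure.** The only power figure is 85% at N=900, f=0.05, correlation 0.5, two measurements, alpha 0.05 (Sample Size Needs). Noncentrality = 900 × 2 × 0.05² / (1 − 0.5) = 9 on 1 and 899 df, which gives power 0.850. It reproduces, but it concerns one topic against control. The SAP states no figure for 1b(i).

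**Inputs.** From the SAP: N=900 (1,000 recruited), six topics, correlation 0.5. Inferred: one AI and one human rating per topic per person. Assumed, as shares of a total rating variance of 1: participant 0.50 (matching the correlation), topic t = 0.03, participant-by-topic pt = 0.06 to 0.20, participant-by-source ps = 0 to 0.05, residual e = the remainder. Pair-to-pair variation in the source difference is set to 0. The base split is pt = 0.12, ps = 0.02, e = 0.33.

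**True variance for the tested messages.** A participant's mean AI-minus-human difference has variance 2ps + 2e/6; topic and participant-by-topic effects cancel. Averaged over N people:

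V_true = (e + 6ps) / (3N)

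**Variance reported by the planned model.** The residual mean square has 11 df per person, and the source coefficient's variance is that mean square divided by 3N:

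V_plan = [e + (10/11)(t + pt) + (6/11)ps] / (3N)

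So the planned SE is too large when t + pt exceeds 6ps, and too small when it is less.

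**Results at N=900 (3N = 2,700).**

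| Split | 2,700 × V_plan | 2,700 × V_true | SE planned / true | Ratio | Rejection at nominal 5% |
|---|---|---|---|---|---|
| ps 0.05, pt 0.06, e 0.36 | 0.36 + 0.082 + 0.027 = 0.469 | 0.36 + 0.30 = 0.66 | 0.0132 / 0.0156 | 0.84 | about 10% |
| Base: ps 0.02, pt 0.12, e 0.33 | 0.33 + 0.136 + 0.011 = 0.477 | 0.33 + 0.12 = 0.45 | 0.0133 / 0.0129 | 1.03 | about 4% |
| ps 0, pt 0.20, e 0.27 | 0.27 + 0.209 = 0.479 | 0.27 | 0.0133 / 0.0100 | 1.33 | about 1% |

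The rejection rate is the two-sided normal tail beyond 1.96 × ratio. Simulation with 4,000 data sets per split agrees: 0.8% to 9.8% at N=900 and 1.1% to 10.3% at N=1,000. The ratio does not depend on N. On a simulated data set, the fitted mixed model and the closed form gave the same SE (0.01328).

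**Absolute size.** The 95% half-width is 1.96 × 0.0133 = 0.026 SD as planned, against 1.96 × 0.0100 = 0.020 to 1.96 × 0.0156 = 0.031 SD in truth. A difference of 0.10 SD has z = 0.10/0.0133 = 7.5 with the planned SE and 6.4 to 10 with the true one, so its verdict would not change.

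**The alternative.** Testing each participant's mean difference rejected 4.6% to 5.9% over all splits and both sample sizes. A model with topic indicators and participant random effects for source and topic rejected 4.6% to 5.8%.

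**Analysis 1b(ii).** With two ratings per person, the random-intercept model is the paired comparison (SE 0.03105 by both routes on a simulated data set). The problem is confined to the pooled test.

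**The case against.** The strongest reply is that no error has been shown. The base split is nearly right, the 1% and 10% figures come from opposite corners of an assumed grid, and the SAP gives no variance components from which to choose. The absolute discrepancy in half-width is under 0.007 SD. The analysis is secondary, and the study calls itself exploratory. All of this stands, and it sets the severity. It does not make the planned SE sound: near-cancellation in one split is not something the plan ensures.

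Two stronger readings are tempting. First, that the test is anti-conservative. The documents do not support a direction; the SE may equally be too wide. Second, that the conclusion concerns AI refinement in general, so that about six message pairs, not 1,000 people, are the sample. A reader might infer this from the objective or from the Introduction: "Another secondary goal is to examine whether warnings refined using AI are perceived as more effective than those selected" in advance. But the Synopsis analysis plan says "Fourth, we will compare social media warnings we refined using AI personas to those we selected", analysis 1b has the same wording, and the data are six named topics. The operative text concerns this team's own messages, and the SAP makes no clear general claim. It also gives no pair-to-pair SD, so an error rate for such a claim would rest on a guess. In addition, 1b(ii) will show whether the difference varies by topic.

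**Conclusion.** The concern holds in a limited form. The SE in 1b(i) is right only if the omitted variation is absent or happens to cancel. Under the assumed shares it is 0.84 to 1.33 times the true SE. The range is not a bound: with no topic or participant-by-topic variation and a between-person SD of 0.4 in the AI-minus-human difference, the ratio is 0.75. Neither the size nor the direction can be read from the SAP, and all figures depend on the inferred design of six complete pairs per participant.

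Only an estimated difference between about 0.020 and 0.031 SD could change verdict over the assumed shares. Paper 1, analysis 1b(ii) and the sample size are unaffected. This is a low-severity improvement to a secondary analysis, worth making because it costs almost nothing.

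**What to change.** In 1b(i), keep the mean AI-minus-human difference as the estimate. Take its SE, confidence interval and p-value from each participant's own mean difference over the six topics, on N − 1 df. With complete ratings the estimate is unchanged and no variance split has to be assumed. If some ratings are missing, fit instead a model with topic indicators and participant-level random effects for both source and topic.

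Add one sentence saying that the result applies to the messages tested, in line with the wording of the Synopsis analysis plan and of 1b.

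The cost is one changed line and one added sentence. No new data are needed, and 1b(ii) stays as planned. The interval may come out slightly wider or narrower than the planned one, depending on which omitted source of variation dominates.
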